**6.4. Exclusion criteria for extension**

Deviations from exclusion criteria are not allowed because they can potentially jeopardize the scientific integrity, regulatory acceptability of the study or subject safety. Therefore, adherence to the criteria as specified in the protocol is essential.

The following criteria should be checked at the time of entry to the extension. If ANY exclusion criterion applies, the subject must not be included in the extension.

**CONFIDENTIAL**209141 (RSV MAT-011)  
Protocol Amendment 6 Final**6.4.1. Medical conditions for extension**

- History of any reaction or hypersensitivity likely to be exacerbated by any component of the vaccines;
- Any confirmed or suspected immunosuppressive or immunodeficient condition, based on medical history and physical examination (no laboratory testing required);
- Hypersensitivity to latex;
- Acute or chronic clinically significant pulmonary, cardiovascular, hepatic or renal functional abnormality, as determined by medical history, physical examination or laboratory screening tests;
- Significant or uncontrolled psychiatric illness;
- Recurrent history or un-controlled neurological disorders or seizures;
- Documented HIV-positive subject;
- History of or current autoimmune disease;
- Body mass index (BMI)  $> 40 \text{ kg/m}^2$ ;
- Participants who experienced any SAE judged to be possibly or probably related to first dose vaccination of RSVPreF3, including hypersensitivity reactions.
- Any other clinical condition that, in the opinion of the investigator, might pose additional risk to the subject due to participation in the study.

**6.4.2. Prior/Concomitant therapy for extension (Amended 09-APR-2021)**

- Use of any investigational or non-registered product (drug, vaccine or medical device) other than the study vaccines during the period starting 30 days before the second dose of study vaccine (Day -29 to Day 1), or planned use during the 6 month study extension period;
- Administration of long-acting immune-modifying drugs at any time during the study period (e.g. infliximab);
- Administration of immunoglobulins and/or any blood products or plasma derivatives during the period starting 3 months before the first dose of study vaccines or planned administration during the study period;
- Chronic administration (defined as more than 14 days in total) of immunosuppressants or other immune-modifying drugs during the period starting 3 months prior to the first vaccine dose(s). For corticosteroids, this will mean prednisone  $\geq 5 \text{ mg/day}$ , or equivalent. Inhaled and topical steroids are allowed;
- Planned administration/administration of a vaccine not foreseen by the study protocol within the period starting 30 days before and ending 30 days after study 2nd dose vaccination\*, with the exception of any licensed influenza vaccine which may be administered  $\geq 15$  days before or after study vaccination.

**\*Note: In case an emergency mass vaccination for an unforeseen public health threat (e.g.: a pandemic) is organised by the public health authorities, outside the**

**CONFIDENTIAL**209141 (RSV MAT-011)  
Protocol Amendment 6 Final

routine immunisation program, the time period described above can be reduced if necessary for that vaccine provided it is licensed and used according to its Summary of Product Characteristics (SmPC) or Prescribing Information and according to the local governmental recommendations.

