## 2. SCHEDULE OF ACTIVITIES (SOA)

**Table 3 Schedule of Activities**

Epoch	Epoch 001	Epoch 002 (Vaccination 1)			Epoch 003 (Follow-up 1)		Epoch 004 (Vaccination 2)				Epoch 005 (Follow-up 2)
Type of contact	Screening	Visit 1	Visit 2	Visit 3	Phone Contact 1		Visit 4	Visit 5	Phone Contact 2	Visit 6	Phone Contact 3
Time points	Day -7 to Day 1	Day 1	Day 8	Day 31	Day 181	Day 181 to -7 before 2 nd vaccination	Day -7 to Day of 2 nd vaccination	From 12 up to 18 months post 1 st vaccination	Day 8 post 2 nd vaccination	Day 31 post 2 nd vaccination	Day 181 post 2 nd vaccination
Sampling time points	Pre-Vacc 1	Vacc 1	Post-Vacc 1	Post-Vacc 1	Post-Vacc 1	Pre-Vacc 2	Pre-Vacc 2	Vacc 2	Post-Vacc 2	Post-Vacc 2	Post-Vacc 2
Informed consent	●						●				
Assign subject number	●										
Check inclusion/exclusion criteria	●	0					●				
Check contraindications to subsequent vaccine(s) administration							0	0			
Phone contact					●				●		●
Collect demographic data	● 										
Medical history	0	●					●				
Physical examination 	●	●	●	0			●			0	
Urine pregnancy test 	●	●						●			
Pre-vaccination body temperature and heart rate		●									
Pre-vaccination vital sign readings 								●			
Distribution of subject card		0						0			

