### **6.2.2. Prior/Concomitant therapy**

- Use of any investigational or non-registered product (drug, vaccine or medical device) other than the study vaccines during the period starting 30 days before the first dose of study vaccines (Day -29 to Day 1), or planned use during the study period;
- Administration of long-acting immune-modifying drugs at any time during the study period (e.g. infliximab);
- Administration of immunoglobulins and/or any blood products or plasma derivatives during the period starting 3 months before the first dose of study vaccines or planned administration during the study period;
- Chronic administration (defined as more than 14 days in total) of immunosuppressants or other immune-modifying drugs during the period starting 3 months prior to the first vaccine dose(s). For corticosteroids, this will mean prednisone  $\geq 5$  mg/day, or equivalent. Inhaled and topical steroids are allowed;
- Planned administration/administration of a vaccine not foreseen by the study protocol within the period starting 30 days before and ending 30 days after study primary vaccination, with the exception of any licensed influenza vaccine which may be administered  $\geq 15$  days before or after study vaccination;
- Administration of a vaccine containing diphtheria, tetanus or pertussis antigens or diphtheria and tetanus toxoids within the previous 5 years (by participant report);
- Previous experimental vaccination against RSV;

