**Table 8      Treatments administered (Part 2)**

Primary Vaccination						
Group	Formulation	N		Laterality		Laterality
XRSV120_dTpa	ex-US	50	RSVPreF3=120µg	Left Arm	dTpa 500	Right Arm
Xplacebo_RSV120		50	RSVPreF3=120µg	Left Arm	Placebo	Right Arm
XRSV60_dTpa		50	RSVPreF3=60µg	Left Arm	dTpa 500	Right Arm
Xplacebo_RSV60		50	RSVPreF3=60µg	Left Arm	Placebo	Right Arm
Xplacebo_dTpa		50	Placebo	Left Arm	dTpa 500	Right Arm
URSV120_dTpa	US	50	RSVPreF3=120µg	Left Arm	dTpa 300	Right Arm
Uplacebo_RSV120		50	RSVPreF3=120µg	Left Arm	Placebo	Right Arm
URSV60_dTpa		50	RSVPreF3=60µg	Left Arm	dTpa 300	Right Arm
Uplacebo_RSV60		50	RSVPreF3=60µg	Left Arm	Placebo	Right Arm
Uplacebo_dTpa		50	Placebo	Left Arm	dTpa 300	Right Arm
2 nd Vaccination						
Groups in primary vaccination	Formulation in primary vaccination	N	Groups in 2 nd vaccination	Laterality		
XRSV120_dTpa	ex-US	50	RSVPreF3=120µg	Non-Dominant		
Xplacebo_RSV120		50	RSVPreF3=120µg	Non-Dominant		
XRSV60_dTpa		50	RSVPreF3=120µg	Non-Dominant		
Xplacebo_RSV60		50	RSVPreF3=120µg	Non-Dominant		
Xplacebo_dTpa		50	RSVPreF3=120µg	Non-Dominant		
URSV120_dTpa	US	50	RSVPreF3=120µg	Non-Dominant		
Uplacebo_RSV120		50	RSVPreF3=120µg	Non-Dominant		
URSV60_dTpa		50	RSVPreF3=120µg	Non-Dominant		
Uplacebo_RSV60		50	RSVPreF3=120µg	Non-Dominant		
Uplacebo_dTpa		50	RSVPreF3=120µg	Non-Dominant		

Note: study groups labeled X = ex-US; study groups labeled U = US.

Refer to the Study Procedures Manual (SPM) for detailed instructions on study vaccine reconstitution.

After completing all prerequisite procedures prior to vaccination (refer to Section 7.7 regarding the contraindications to subsequent vaccination), the assigned study vaccines (Table 9) will be administered as shown in Table 7 and Table 8.

If the investigator or delegate determines that the subject's health on the day of administration temporarily precludes vaccine(s) administration, the visit will be rescheduled within the allowed interval for this visit (refer to Table 4).

The subjects will be observed closely for at least 60 minutes following the administration of the vaccine(s), with appropriate medical treatment readily available in case of anaphylaxis and syncope.

**CONFIDENTIAL**209141 (RSV MAT-011)  
Protocol Amendment 6 Final

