## **7.7. Contraindications to subsequent vaccine(s) administration**

N/A

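### Protocol 6.4.2 dates two of its five second-dose exclusions from the first dose, so neither works as a 3-month look-back before dose 2

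*Protocol*

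**What the plan says.** Section 6.4.2 of the protocol governs prior and concomitant therapy for the extension. Its item on investigational products is dated from the new dose: "during the period starting 30 days before the second dose of study vaccine (Day -29 to Day 1"). Its item on non-study vaccines is likewise tied to the second vaccination. Long-acting immune-modifying drugs are barred throughout the study period.

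The remaining two items point to the first dose. Immunoglobulins, blood products and plasma derivatives are excluded "during the period starting 3 months before the first dose of study vaccines or planned administration during the study period". Chronic immunosuppressants, meaning more than 14 days in total, are excluded "during the period starting 3 months prior to the first vaccine dose(s").

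Section 6.2.2 uses the same wording for the primary study, for example "Administration of immunoglobulins and/or any blood products or plasma derivatives during the period starting 3 months before the first dose of study vaccines".

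Section 6.4 has the criteria checked on entry to the extension, allows no deviations, and adds: "If ANY exclusion criterion applies, the subject must not be included in the extension". Table 4 places Visit 5 (dose 2) 365 to 548 days after Visit 1 (dose 1).

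**The concern.** An exclusion for recent immunosuppression or recent blood products should look back from the dose whose response is to be measured. These two items look back from a dose given at least a year earlier, while two neighbouring items in the same list were re-dated to dose 2. Amendment 6 reopened 6.4.2 to add the mass-vaccination note and left these two anchors unchanged. The pattern suggests carry-over from 6.2.2 rather than a design choice, although the documents do not say so.

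At stake are a uniform eligibility rule for the second dose and a clean basis for the Visit 4 (persistence) and Visit 6 (31 days after dose 2) samples, which serve secondary immunogenicity objectives.

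**Working it through.** The plan gives no figure to reproduce. The check is a comparison of text plus arithmetic on the Table 4 interval.

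**1. Anchors in 6.4.2**

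| Item | Dated from |
|---|---|
| Investigational or non-registered product | Dose 2 |
| Long-acting immune-modifying drugs | Study period |
| Immunoglobulins, blood products, plasma derivatives | Dose 1, or planned use in the study period |
| Chronic immunosuppressants | Dose 1 |
| Non-study vaccines | Dose 2 |

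Two items are anchored to dose 2, one to the study period and two to dose 1.

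**2. Where the window ends.** Neither 6.4.2 nor 6.2.2 states an end. For the primary study the period stops at enrolment in effect, because 6.2 has its criteria checked at study entry. The parallel rule in 6.4 is a check at extension entry, which favours a window running up to that point. Against this, the neighbouring item on long-acting drugs says outright that it covers the whole study period, and these two do not.

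**3. Length of look-back before dose 2**

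- Window closes at dose 1: it ends 365 to 548 days before dose 2. A woman enrolled in compliance with 6.2.2 cannot newly meet it. Only the planned-use limb for immunoglobulins still operates; the immunosuppressant item has no such limb.
- Window runs to extension entry: 3 + 12 = 15 months to 3 + 18 = 21 months. Relative to the dose-1 rule, 15/3 = 5 and 21/3 = 7 times as long. The threshold of more than 14 days in total would also accumulate over that whole stretch.

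**4. Consequences**, for a woman with more than 14 days of an immunosuppressant who meets no other exclusion:

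| Timing of exposure | Closes at dose 1 | Runs to extension entry | Re-dated to dose 2 |
|---|---|---|---|
| Within 3 months before dose 2 | Eligible | Barred | Barred |
| Between doses, more than 3 months before dose 2 | Eligible | Barred | Eligible |
| Within 3 months before dose 1 | Already excluded by 6.2.2 | Already excluded by 6.2.2 | Already excluded by 6.2.2 |

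Neither reading of the current text gives the last column. An example for the first row is 3 weeks of prednisone at 5 mg/day or more, ended a month before dose 2, for a condition not listed in 6.4.1.

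**5. What is recorded.** Section 7.5.1 has sites ask about all medication at each contact. What it requires in the eCRF is mainly the 31 days after each dose, plus products causing withdrawal or non-eligibility and those linked to an SAE. There is no follow-up between Phone Contact 1 and Visit 4, and for that gap 8.3.2 names conditions and vaccinations, not drugs. Table 3 marks medication recording at Visit 4, but its footnote refers back to 7.5. An exposure in the gap that does not bar entry therefore need not be recorded. Yet 7.5.2 and SAP Table 4 (code 2040, applicable at Visits 4 and 6) make such exposures possible grounds for per-protocol elimination.

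**The case against.** The strongest reply is that the open-ended reading is both natural and harmless. It follows from the check at extension entry in 6.4, bars the recent prednisone user, agrees with the study-period ban on long-acting drugs, and keeps exposures that could distort the persistence sample out of the extension. Much of this stands. A reader might infer that recent users will be dosed, that none of the 3 months before dose 2 is covered, or that sites will give opposite decisions. Those outcomes require a site to close the window at dose 1. They are possible, not expected.

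The reply does not rescue the text. The open-ended reading still bars women for exposures up to 21 months old. It is not needed to protect the Visit 4 sample, because per-protocol elimination already addresses exposure between doses. Other cover is real but partial: 6.3 requires that the woman remain healthy, 6.4.1 excludes immunosuppressive conditions, autoimmune disease and investigator-judged risk, and 7.6 has intercurrent conditions recorded. None of these sets a drug look-back before dose 2.

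A second tempting inference is that dose 2 goes unchecked. Section 7.1 tells sites to "refer to Section 7.7 regarding the contraindications to subsequent vaccination", Table 3 schedules "Check contraindications to subsequent vaccine(s) administration" at Visits 4 and 5, and 7.7 reads only N/A. The documents do not support that inference: 6.4, 6.5, the precautions check in 7.8 and the pregnancy test in 8.3.4 all still apply. Section 7.7 is a dead cross-reference. Nor does the absence of an inclusion/exclusion mark at Visit 5 show a gap. Visit 4 is normally at most 7 days earlier (30 under special circumstances), and Visit 5 has its own contraindication check, pregnancy test and vital signs.

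**Conclusion.** The point holds as a misstated eligibility rule. Two of the five exclusions in 6.4.2 carry the wrong anchor for a second-dose decision. As written they either add nothing for a compliantly enrolled woman, apart from planned immunoglobulin use, or reach back 15 to 21 months. Neither is the 3-month look-back used for dose 1.

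Severity is minor. Dose-1 safety and immunogenicity are unaffected, and the possible effect is confined to entry to the extension and the Visit 4 and Visit 6 samples. The documents give neither a consent rate for the extension nor a frequency for these exposures, so the number of women affected cannot be estimated.

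The conclusion rests on two assumptions: that the intended rule was a look-back of the same length as for dose 1, and that the study period in 7.5.2 includes the interval between Phone Contact 1 and Visit 4.

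**What to change.** - **6.4.2:** in the immunoglobulin and immunosuppressant items, replace the reference to the first dose with the second dose of study vaccine, so that both become 3-month look-backs before dose 2.
- **7.5.1:** add immunosuppressants, immunoglobulins and blood products used between Phone Contact 1 and dose 2 to the items that must be recorded. The re-dated exclusion and the elimination under 7.5.2 and SAP code 2040 can then be applied from data.
- **Tidying only:** replace N/A under "Contraindications to subsequent vaccine(s) administration" (7.7) with a reference to 6.4 and 6.5.

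The cost is amendment wording and one recording item for a question that sites already ask. There is a small downside: women exposed between doses, but more than 3 months before dose 2, may enter. Their Visit 4 and Visit 6 samples would be handled by per-protocol elimination.

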#### **6.4.3. Prior/Concurrent clinical study experience for extension**

- Concurrently participating in another clinical study, at any time during the study period, in which the subject has been or will be exposed to an investigational or a non-investigational vaccine/product (drug or medical device);

#### **6.4.4. Other exclusions for extension**

- Pregnant or lactating female at the time of Visit 4;
- Female planning to become pregnant or planning to discontinue contraceptive precautions;
- History of alcoholism, drug abuse and/or use disorder within the past two years (as defined in DSM-5 Diagnostic Criteria) [Camargo, 1984; Christy, 1995; Hasin, 2013];
- Any study personnel or their immediate dependents, family, or household members.

#### **6.5. Criteria for temporary delay for enrolment and vaccination**

Vaccination may be postponed within the allowed time interval until transient circumstances cited below have been resolved:

- Haematological/biochemical values out of normal range at screening, *if* expected to be temporary. Subjects must be re-screened at a later date within the allowed time interval.
- Acute disease and/or fever at the time of enrollment;
  - Fever is defined as body temperature  $\geq 38^{\circ}\text{C}/100.4^{\circ}\text{F}$ . The preferred location for measuring temperature in this study will be the oral cavity.
  - For subjects with acute disease and/or fever at the time of enrollment, Visit 1 for primary vaccination and Visit 5, the 2nd vaccination will be rescheduled within the allowed window for the visit.
  - Screening hematological/biochemical do not need to be repeated if obtained within 30 days of each vaccination.

Subjects with a minor illness (such as mild diarrhea, mild upper respiratory infection) without fever may be enrolled at the discretion of the investigator.

#### **6.6. Screen and baseline failures**

“Screening failures” are subjects who withdraw or are withdrawn from the study after giving informed consent, but before study eligibility (presence of all inclusion and absence of all exclusion criteria) is confirmed.

**CONFIDENTIAL**209141 (RSV MAT-011)  
Protocol Amendment 6 Final

Discovery during screening of any condition that violates the requirements for study eligibility should be considered a screening failure. Discovery during Visit 1 of any condition that violates the requirements for study eligibility should also be considered a screening failure. Limited data for screening failures (including reason for screening failure and any SAEs that occurred at the visit) will be collected and reported in the eCRF.

The development of such conditions (after Visit 1) does not constitute screening failure and should be captured on the eCRF, as applicable.

## 6.7. Screen failures to the extension

“Screening failures” for the extension are subjects who withdraw or are withdrawn from the extension after giving informed consent to the extension, but before extension eligibility (presence of all inclusion and absence of all exclusion criteria) is confirmed. Limited data for screening failures (including reason for screening failure and any SAEs that occurred at the visit) will be collected and reported in the eCRF.

# 7. TREATMENTS

Study treatment is defined as a set of investigational product(s) or marketed product(s) or placebo intended to be administered to a subject.

## 7.1. Treatments administered

**Table 7** Treatments administered (Part 1)

	RSV MAT 120	RSV MAT 60	Boostrix-ex-US (dTpa_500)	Boostrix-US (dTpa_300)	Placebo
Vaccines /Products	RSVPreF3 high dose	RSVPreF3 mid dose	dTpa	dTpa	NaCl
	NaCl	NaCl			
Presentation	Powder for suspension for injection (vial) (174mcg/vial)	Powder for suspension for injection (vial) (87mcg/vial)	Suspension for injection (syringe)	Suspension for injection (syringe)	Solution for injection; vial)
	Solution for solution for injection; (vial)	Solution for solution for injection; (vial)			
Formulation	RSVPreF3(120 µg)/Trehalose(12.73 mg).  NaCl solution (4.5 mg/0.5 mL, ~150 mM)	RSVPreF3(60 µg)/Trehalose(6.42 mg).  NaCl solution (4.5 mg/0.5 mL, ~150 mM)	Diphtheria toxoid ( $\geq$ 2 IU) adsorbed on aluminium hydroxide and aluminium phosphate; Tetanus toxoid ( $\geq$ 20 IU) adsorbed on aluminium	Diphtheria toxoid ( $\geq$ 2 IU) adsorbed on aluminium hydroxide; Tetanus toxoid ( $\geq$ 20 IU) adsorbed on aluminium	NaCl solution (4.5 mg/0.5 mL, ~150 mM)

## CONFIDENTIAL

209141 (RSV MAT-011)  
Protocol Amendment 6 Final

	RSV MAT 120	RSV MAT 60	Boostrix-ex-US (dTpa_500)	Boostrix-US (dTpa_300)	Placebo
			adsorbed on aluminium hydroxide and aluminium phosphate; Pertussis toxoid (8 µg) adsorbed on aluminium hydroxide and aluminium phosphate; Filamentous haemagglutinin (8 µg) adsorbed on aluminium hydroxide and aluminium phosphate; Pertactin (69 kDa outer membrane protein) (2.5 µg) adsorbed on aluminium hydroxide and aluminium phosphate; Aluminium hydroxide (0.3 mg Al 3+ ); Aluminium phosphate (0.2 mg Al 3+ ); Sodium chloride; Water for injections q.s. 0.5 mL	hydroxide; Pertussis toxoid (8 µg) adsorbed on aluminium hydroxide; Filamentous haemagglutinin (8 µg) adsorbed on aluminium hydroxide; Pertactin (69 kDa outer membrane protein) (2.5 µg) adsorbed on aluminium hydroxide; Aluminium hydroxide (0.3 mg Al 3+ ); Sodium chloride (4.4 mg); Water for injections q.s. 0.5 mL	
Route of Administration	Intramuscular use	Intramuscular use	Intramuscular use	Intramuscular use	Intramuscular use
Administration site					
Location	Deltoid	Deltoid	Deltoid	Deltoid	Deltoid
Laterality	Refer to Table 8 .				
No of doses	2	1	1	1	1
Dose volume	0.5 ml	0.5 ml	0.5 ml	0.5 ml	0.5 ml
Packaging and Labelling	Refer to the SPM	Refer to the SPM	Refer to the SPM	Refer to the SPM	Refer to the SPM
Manufacturer	RSVPreF3: GSK Biologicals NaCl: GSK Biologicals	RSVPreF3: GSK Biologicals NaCl: GSK Biologicals	GSK Biologicals	GSK Biologicals	GSK Biologicals

**CONFIDENTIAL**209141 (RSV MAT-011)  
Protocol Amendment 6 Final

The vaccinations will be administered in each arm as follows:

**Table 8      Treatments administered (Part 2)**

Primary Vaccination						
Group	Formulation	N		Laterality		Laterality
XRSV120_dTpa	ex-US	50	RSVPreF3=120µg	Left Arm	dTpa 500	Right Arm
Xplacebo_RSV120		50	RSVPreF3=120µg	Left Arm	Placebo	Right Arm
XRSV60_dTpa		50	RSVPreF3=60µg	Left Arm	dTpa 500	Right Arm
Xplacebo_RSV60		50	RSVPreF3=60µg	Left Arm	Placebo	Right Arm
Xplacebo_dTpa		50	Placebo	Left Arm	dTpa 500	Right Arm
URSV120_dTpa	US	50	RSVPreF3=120µg	Left Arm	dTpa 300	Right Arm
Uplacebo_RSV120		50	RSVPreF3=120µg	Left Arm	Placebo	Right Arm
URSV60_dTpa		50	RSVPreF3=60µg	Left Arm	dTpa 300	Right Arm
Uplacebo_RSV60		50	RSVPreF3=60µg	Left Arm	Placebo	Right Arm
Uplacebo_dTpa		50	Placebo	Left Arm	dTpa 300	Right Arm
2 nd Vaccination						
Groups in primary vaccination	Formulation in primary vaccination	N	Groups in 2 nd vaccination	Laterality		
XRSV120_dTpa	ex-US	50	RSVPreF3=120µg	Non-Dominant		
Xplacebo_RSV120		50	RSVPreF3=120µg	Non-Dominant		
XRSV60_dTpa		50	RSVPreF3=120µg	Non-Dominant		
Xplacebo_RSV60		50	RSVPreF3=120µg	Non-Dominant		
Xplacebo_dTpa		50	RSVPreF3=120µg	Non-Dominant		
URSV120_dTpa	US	50	RSVPreF3=120µg	Non-Dominant		
Uplacebo_RSV120		50	RSVPreF3=120µg	Non-Dominant		
URSV60_dTpa		50	RSVPreF3=120µg	Non-Dominant		
Uplacebo_RSV60		50	RSVPreF3=120µg	Non-Dominant		
Uplacebo_dTpa		50	RSVPreF3=120µg	Non-Dominant		

Note: study groups labeled X = ex-US; study groups labeled U = US.

Refer to the Study Procedures Manual (SPM) for detailed instructions on study vaccine reconstitution.

After completing all prerequisite procedures prior to vaccination (refer to Section 7.7 regarding the contraindications to subsequent vaccination), the assigned study vaccines (Table 9) will be administered as shown in Table 7 and Table 8.

If the investigator or delegate determines that the subject's health on the day of administration temporarily precludes vaccine(s) administration, the visit will be rescheduled within the allowed interval for this visit (refer to Table 4).

The subjects will be observed closely for at least 60 minutes following the administration of the vaccine(s), with appropriate medical treatment readily available in case of anaphylaxis and syncope.

**CONFIDENTIAL**209141 (RSV MAT-011)  
Protocol Amendment 6 Final

